6.5.1 Rescue Medications and Supportive Care

No rescue or supportive medications are specified for use in this study.

6.6 Dose Modification

No dose modification is allowed in this study.

6.6.1 Stopping Rules

There are no prespecified stopping rules for this study.

6.7 Intervention After the End of the Study

There is no study-specified intervention after the end of the study.

6.8 Clinical Supplies Disclosure

This study is blinded but supplies are provided as open label; therefore, an unblinded pharmacist or qualified study-site personnel will be used to blind supplies. Study intervention identity (name, strength, or potency) is included in the label text; random code/disclosure envelopes or lists are not provided.

The emergency unblinding call center will use the intervention/randomization schedule for the study to unblind participants and to unmask study intervention identity. The emergency unblinding call center should only be used in cases of emergency (see Section 8.1.12). If the emergency unblinding call center is not available for a given site in this study, the central electronic intervention randomization system (IRT) should be used to unblind participants and to unmask study intervention identity. The Sponsor will not provide random code/disclosure envelopes or lists with the clinical supplies.

See Section 8.1.12 for a description of the method of unblinding a participant during the study, should such action be warranted.

6.9 Standard Policies

Not applicable.

7 DISCONTINUATION OF STUDY INTERVENTION AND PARTICIPANT WITHDRAWAL

7.1 Discontinuation of Study Intervention

In clinical studies with a single intervention, discontinuation of study intervention can only occur before the intervention and generally represents withdrawal from the study.

Participants who receive a single-dose intervention cannot discontinue study intervention.

7.2 Participant Withdrawal From the Study

A participant must be withdrawn from the study if the participant or participant's legally acceptable representative withdraws consent/assent from the study.

If a participant withdraws from the study, they will no longer receive study intervention or be followed at scheduled protocol visits.

Specific details regarding procedures to be performed at the time of withdrawal from the study, as well as specific details regarding withdrawal from FBR, are outlined in Section 8.1.11. The procedures to be performed should a participant repeatedly fail to return for scheduled visits and/or if the study site is unable to contact the participant/participant's legally acceptable representative are outlined in Section 7.3.

7.3 Lost to Follow-up

If a participant fails to return to the clinic for a required study visit and/or if the site is unable to contact the participant/participant's legally acceptable representative, the following procedures are to be performed:

- The site must attempt to contact the participant/participant's legally acceptable representative and reschedule the missed visit. If contacted, the participant/participant's legally acceptable representative should be counseled on the importance of maintaining the protocol-specified visit schedule.
- The investigator or designee must make every effort to regain contact with the participant/participant's legally acceptable representative at each missed visit (eg, telephone calls and/or a certified letter to the participant's last known mailing address or locally equivalent methods). These contact attempts should be documented in the participant's medical record.

8 STUDY ASSESSMENTS AND PROCEDURES

- Study procedures and their timing are summarized in the SoA.
- Adherence to the study design requirements, including those specified in the SoA, is essential and required for study conduct.
- The investigator is responsible for ensuring that procedures are conducted by appropriately qualified (by education, training, and experience) staff. Delegation of study-site personnel responsibilities will be documented in the Investigator Trial File Binder (or equivalent).
- All study-related medical decisions must be made by an investigator who is a qualified physician.
- All screening evaluations must be completed and reviewed to confirm that potential participants meet all eligibility criteria. The investigator will maintain a screening log to record details of all participants screened and to confirm eligibility or record reasons for screening failure, as applicable.
- Procedures conducted as part of the participant's routine clinical management (eg, blood count) and obtained before providing documented informed consent/assent may be used for screening or baseline purposes provided the procedures meet the protocol-specified criteria and were performed within the time frame defined in the SoA.
- Additional evaluations/testing may be deemed necessary by the investigator and or the Sponsor for reasons related to participant safety. In some cases, such evaluation/testing may be potentially sensitive in nature (eg, HIV, hepatitis C), and thus local regulations may require that additional informed consent/assent be obtained from the participant (or participant's legally acceptable representative). In these cases, such evaluations/testing will be performed in accordance with those regulations.
- The maximum amount of blood collected from each participant over the duration of the study will not exceed the volume mentioned in Appendix 2.
- Repeat or unscheduled samples may be taken for safety reasons or for technical issues with the samples.

8.1 Administrative and General Procedures

8.1.1 Informed Consent

The investigator or medically qualified designee (consistent with local requirements) must obtain documented informed consent, or assent if applicable, from each potential participant (or their legally acceptable representative) prior to participating in this clinical study or FBR. If there are changes to the participant's status during the study (eg, health or age of majority requirements), the investigator or medically qualified designee must ensure the appropriate documented informed consent/assent is in place.

8.1.1.1 General Informed Consent

Informed consent/assent given by the participant or their legally acceptable representative must be documented on an ICF. The form must include the study protocol number, study

protocol title, dated signature, and agreement of the participant (or his/her legally acceptable representative) and of the person conducting the consent/assent discussion.

A copy of the signed and dated ICF should be given to the participant (or their legally acceptable representative) before participation in the study.

The initial ICF, any subsequent revised ICF, and any written information provided to the participant or their legally acceptable representative must receive the IRB/IEC's approval/favorable opinion in advance of use. The participant or his/her legally acceptable representative should be informed in a timely manner if new information becomes available that may be relevant to the willingness of the participant or their legally acceptable representative to continue participation in the study. The communication of this information will be provided and documented via a revised ICF or addendum to the original ICF that captures the participant's or the participant's legally acceptable representative's dated signature.

Specifics about the study and the study population are to be included in the study ICF.

Informed consent/assent will adhere to IRB/IEC requirements, applicable laws and regulations, and Sponsor requirements.

8.1.1.2 Consent and Collection of Specimens for Future Biomedical Research

The investigator or medically qualified designee will explain the FBR consent/assent to the participant, or the participant's legally acceptable representative, answer all of his/her questions, and obtain documented informed consent/assent before performing any procedure related to FBR. A copy of the informed consent/assent will be given to the participant (or participant's legally acceptable representative) before performing any procedure related to FBR.

8.1.2 Inclusion/Exclusion Criteria

All inclusion and exclusion criteria will be reviewed by the investigator, who is a qualified physician, to ensure that the participant qualifies for the study.

8.1.3 Participant Identification Card

All participants (or participant's legally acceptable representative) will be given a participant identification card identifying them as participants in a research study. The card will contain study-site contact information (including direct telephone numbers) to be used in the event of an emergency. The investigator or qualified designee will provide the participant (or participant's legally acceptable representative) with a participant identification card immediately after documented informed consent/assent is provided. At the time of intervention randomization, site personnel will add the treatment/randomization number to the participant identification card.

The participant ID card also contains contact information for the emergency unblinding call center so that a health care provider can obtain information about study intervention in emergency situations where the investigator is not available.

8.1.4 Medical History

A medical history will be obtained by the investigator or qualified designee. The participant's relevant medical history for the 5 years before Visit 1 will be obtained to ensure that the participant satisfies the inclusion and exclusion criteria of the study.

8.1.5 Prior and Concomitant Medications Review

8.1.5.1 Prior Medications

The following must be documented by the investigator or qualified designee before vaccination at Visit 1 and recorded on the appropriate eCRF:

- Prior vaccinations and medication taken by the participant within 30 days before study vaccination at Visit 1.
- Any prior pneumococcal vaccination regardless of timing prior to Visit 1.
- Any analgesic or antipyretic medication taken on the day of vaccination before vaccination.

8.1.5.2 Concomitant Medications

The participant/participant's legally acceptable representative will use the eVRC (Section 8.1.10) to record concomitant medications (including the use of any analgesic or antipyretic medication) and nonstudy vaccinations received from the day of vaccination through 30 days postvaccination.

The investigator or qualified designee must record concomitant medications and nonstudy vaccinations on the appropriate eCRF through Day 30 after vaccination. Outside this period, report only concomitant medications related to an SAE.

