1.3 Schedule of Activities

Study Period:	Intervention and Follow-up					Notes
Visit Number:	1	2	3	4	5	
Visit Type:	Visit	TC	Visit	TC	TC	
Study Day:	Day 1	Day 7	Day 30	Day 90	Day 180	
Visit Window:	-	Day 7 to Day 10	Day 30 to Day 44	Day 76 to Day 104	Day 166 to Day 194	
Administrative Procedures						
Screening Procedures						
Informed Consent/Assent	X					Must be obtained before any study procedures are conducted.
Informed Consent/Assent for Optional FBR	X					Must be obtained before FBR sample collection.
Assignment of Screening Number	X					
Participant Identification Card	X					
Inclusion/Exclusion Criteria	X					
Medical History	X					
Postrandomization Procedures						
Assignment of Randomization Number	X					
Prior/Concomitant Medication and Nonstudy Vaccination Review	X	X	X	X	X	
V116/PPSV23 Administration (blinded)	X					
Provide Electronic Device (if needed) or Configure Device (Personal or Provisioned) for eVRC Data Collection	X					Instructions for using the eVRC will be reviewed with the participant or participant's legally acceptable representative.
Review eVRC Data With Participant or Participant's LAR		X	X			
Collect Electronic Device From Participant or Participant's Legally Acceptable Representatives Who Received an Electronic Device or Deactivate Personal Devices			X			
Complete Telephone Contact Questionnaire				X	X	
Safety Procedures						
Complete Physical Examination	X					Performed by investigator or medically qualified designee before vaccination.
Pregnancy Test (if applicable)	X					Participants of childbearing potential must have a negative urine or serum test (consistent with local requirements and sensitive to ≤ 25 IU hCG) result before vaccination.

Study Period:	Intervention and Follow-up					Notes
Visit Number:	1	2	3	4	5	
Visit Type:	Visit	TC	Visit	TC	TC	
Study Day:	Day 1	Day 7	Day 30	Day 90	Day 180	
Visit Window:	-	Day 7 to Day 10	Day 30 to Day 44	Day 76 to Day 104	Day 166 to Day 194	
Body Temperature Measurement	X					Measured before vaccination. Participants with febrile illness (temperature $\geq 100.4^{\circ}\text{F}$ [$\geq 38.0^{\circ}\text{C}$]) within 72 hours before vaccination must be rescheduled.
Postvaccination Observation Period	X					Observed by blinded study-site personnel for at least 30 minutes postvaccination.
AE Monitoring	X	X	X	X	X	Nonserious AEs collected through Day 30 postvaccination; all SAEs and deaths collected through Day 180.
Immunogenicity Assessments						

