15. Is expected to receive any pneumococcal vaccine during the study outside of the protocol.

16. *Received or is scheduled to receive systemic corticosteroids (total daily dose prednisone equivalent of ≥ 2 mg/kg or ≥ 20 mg/day for children > 10 kg) for ≥ 14 consecutive days and has not completed intervention ≥ 14 days before receipt of study vaccine (Day 1) and through 30 days following vaccination. **Note:** Physiologic replacement doses (prednisone equivalent of approximately 5 mg/day), topical, ophthalmic, intraarticular or soft-tissue (eg, bursa, tendon steroid injections), and inhaled/nebulized steroids are permitted.

17. Is currently receiving systemic immunosuppressive therapy, including chemotherapeutic agents or other immunotherapies/immunomodulators used to treat cancer or other conditions, and interventions associated with organ or bone marrow transplantation, or autoimmune disease.

18. *Received any nonlive vaccine ≤ 14 days before receipt of study vaccine or is scheduled to receive any nonlive vaccine ≤ 30 days after receipt of study vaccine. Exception: Inactivated influenza vaccine and SARS-CoV-2 mRNA or SARS-CoV-2 protein subunit vaccine may be administered but must be given ≥ 7 days before or ≥ 15 days after receipt of study vaccine.

19. *Received any live virus vaccine (including SARS-CoV-2 live virus vaccines) ≤ 30 days before receipt of study vaccine or is scheduled to receive any live virus vaccine ≤ 30 days after receipt of study vaccine.

20. Received a blood transfusion or blood products, including immunoglobulin ≤ 6 months before receipt of study vaccine or is scheduled to receive a blood transfusion or blood product ≤ 30 days after receipt of study vaccine. Autologous blood transfusions are not considered an exclusion criterion.

21. Receiving chronic home oxygen therapy.

Prior/Concurrent Clinical Study Experience

22. Is currently participating in or has participated in an interventional clinical study with an investigational compound or device within 2 months of participating in this current study.

Diagnostic Assessments

Not Applicable.

Other Exclusions

23. In the opinion of the investigator, has a history of clinically relevant drug or alcohol use that may interfere with participation in protocol-specified activities.

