6.5 Concomitant Therapy

Medications or vaccinations specifically prohibited in the exclusion criteria are not allowed during the ongoing study (Section 5.2).

If there is a clinical indication for any medications or vaccinations specifically prohibited, the investigator should discuss any questions regarding this with the Sponsor Clinical Director. The final decision on any supportive therapy or vaccination rests with the investigator and/or the participant's primary physician. However, the decision to continue the participant on study intervention requires the mutual agreement of the investigator, the Sponsor, and the participant/participant's legally acceptable representative.

It is important to record the use of any analgesic or antipyretic medication that occurs on the day of vaccination on the eVRC and appropriate eCRF.

Listed below are specific restrictions for concomitant therapy or vaccination:

- Administration of a nonstudy pneumococcal vaccine is prohibited during the study.
- Nonstudy vaccines may only be administered before or after the receipt of study vaccine according to the time frames specified in the Exclusion Criteria (Section 5.2).
- Receipt of systemic corticosteroids (total daily dose prednisone equivalent of ≥ 2 mg/kg or ≥ 20 mg/day for children > 10 kg) for ≥ 14 consecutive days is prohibited from 14 days before vaccination through 30 days following vaccination. **Note:** Physiologic replacement doses (prednisone equivalent of approximately 5 mg/day), topical, ophthalmic, intraarticular or soft-tissue (eg, bursa, tendon steroid injections), and inhaled/nebulized steroids are permitted.

Any deviation from the above requires consultation between the investigator and the Sponsor and written documentation of the collaborative decision on participant management.

Use of prior and concomitant medications/vaccinations should be recorded as described in Section 8.1.5.

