9.4 Analysis Populations

9.4.1 Immunogenicity Analysis Populations

The PP population will serve as the primary population for the immunogenicity endpoint(s). The PP population excludes participants due to important deviations from the protocol that

may substantially affect the results of the primary immunogenicity endpoint(s). Potential deviations that may result in the exclusion of a participant from the PP population include:

- Failure to receive study vaccine at Visit 1 (Day 1)
- Failure to receive correct clinical material as per randomization schedule
- Receipt of a prohibited medication or prohibited vaccine prior to study vaccination

Additional potential deviations that may result in the exclusion of a participant from the PP population for specific immunogenicity analyses (depending on the time point) include:

- Receipt of a prohibited medication or prohibited vaccine prior to a blood sample collection
- Collection of a blood sample outside the prespecified window

The final determination on important protocol deviations, and thereby the composition of the PP population, will be made prior to the final unblinding of the database and will be documented in a separate memo.

A supportive analysis using the FAS population will also be performed for the primary immunogenicity endpoint. The FAS population consists of all randomized participants who received at least 1 study vaccination and have at least 1 serology result. Participants will be included in the vaccination group to which they are randomized for the analysis of the immunogenicity data using the FAS population.

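### Does ending routine medication and vaccination recording at Day 30 weaken the per-protocol set when the primary sample may be drawn up to Day 44?

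*Combined protocol and SAP*

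**What the plan says.** Section 8.1.5.2 sets the recording period. The participant or representative uses the eVRC for medications and nonstudy vaccinations up to 30 days postvaccination. The investigator enters them "on the appropriate eCRF through Day 30 after vaccination. Outside this period, report only concomitant medications related to an SAE".

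The Schedule of Activities (Section 1.3) gives Visit 3, where the second serum sample is taken, a window of "Day 30 to Day 44". The same table lists a "Prior/Concomitant Medication and Nonstudy Vaccination Review" and marks it at all five contacts, Visit 3 included.

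Section 6.5 states: "Administration of a nonstudy pneumococcal vaccine is prohibited during the study". That ban has no 30-day end. The section adds: "Any deviation from the above requires consultation between the investigator and the Sponsor and written documentation".

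Section 9.4.1 names "Receipt of a prohibited medication or prohibited vaccine prior to a blood sample collection" among the deviations that may remove a participant from the PP population for a given time point. PP is the primary population for H1 and H2.

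**The concern.** The PP rule runs to the blood draw, but the record one would expect to support it stops at Day 30. A child bled on Day 30 has complete routine recording up to the sample, and a child bled on Day 44 does not. If a pneumococcal vaccine given in between went unnoticed, its effect on titers would be credited to the study vaccine in the primary analysis.

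The protocol itself treats this exposure as important. Earlier pneumococcal vaccination is documented whatever its date (Section 8.1.5.1), and it is a stratification factor. Section 6.5 sends recording back to Section 8.1.5 and sets no longer period. The planned FAS analysis would not expose the problem either, because a missed exposure would sit in both populations.

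**Working it through.** **1. Length of the interval.** The window, Study Days 30 to 44, has 15 days.

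- Recording through Study Day 30: gap = d − 30 for a draw on day d, so 0 to 14 days. The gaps sum to 105, and 105/15 = 7.0 days on average if draws spread evenly (assumption). On 14 of the 15 days there is some gap.
- Recording through 30 days after a Day 1 vaccination, that is Study Day 31: gap = max(0, d − 31), so 0 to 13 days. The gaps sum to 91, and 91/15 = 6.1 days on average. On 13 of the 15 days there is some gap.

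**2. Exposures that fall in it.** Only a prohibition that continues past 30 days matters.

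- Systemic corticosteroids, live and nonlive vaccines, and blood products: the restrictions in Sections 5.2 and 6.5 end at 30 days after vaccination, so they are essentially covered.
- Immunosuppressive therapy: criterion 17 is worded for entry ("Is currently receiving systemic immunosuppressive therapy, including chemotherapeutic agents"), and its EEA version looks back 6 months from vaccination. It reaches on-study use only through the general opening sentence of Section 6.5.
- Nonstudy pneumococcal vaccine: prohibited throughout the study, so it is clearly affected. Criterion 15 already excludes children expected to receive one.

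**3. Whether the PP rule can still be applied.** The vaccination review is scheduled at Visit 3, and Section 8 makes adherence to the Schedule of Activities a requirement. The site must therefore ask about nonstudy vaccination at the visit where blood is taken. Once reported, a pneumococcal vaccine is a deviation from the first restriction listed in Section 6.5, which requires consultation with the Sponsor and a written record. Section 9.4.1 builds the PP population from important protocol deviations, decided before final unblinding and documented in a memo. It does not say that membership is derived from the Section 8.1.5.2 entries alone.

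**4. Possible size.** The documents give no exposure frequency, so this step is illustration only. Assume a fraction p of one arm, and none of the other, has an unrecorded 4-fold titer change. The GMT ratio then shifts by a factor 4^p.

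- p = 0.5%: 4^0.005 = 1.007 (about 2 of 443 V116 or 1 of 295 PPSV23 participants).
- p = 2%: 4^0.02 = 1.028 (about 9 of 443 or 6 of 295).

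Section 9.8.1 gives lowest planned ratios of 0.84 (common serotypes) and 2.90 (unique serotypes). Pair these with the largest SDs listed there (assumption), and use a normal approximation without the baseline gain from the cLDA model:

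- Common: SE = √(1.43²/443 + 1.43²/295) = 0.1075. Expected lower bound = 0.84 × exp(−1.96 × 0.1075) = 0.680. After the 2% shift, 0.680/1.028 = 0.66, against a margin of 0.5.
- Unique: SE = √(1.52²/443 + 2.54²/295) = 0.1646. Expected lower bound = 2.90 × exp(−1.96 × 0.1646) = 2.100. After the 2% shift, 2.100/1.028 = 2.04, against a margin of 2.0.

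The second pairing looks harsher than the plan. With no shift at all it gives Φ(ln(2.90/2.0)/0.1646 − 1.96) = Φ(0.297), about 62% power for one serotype, against more than 90% claimed in Section 9.8.1 for all 21 together. A stray PPSV23 dose would also have limited reach into H2: its listed antigens include none of the nine unique serotypes, although 15B is related to 15C. Equal exposure in both arms with the same fold change would cancel.

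**The case for a change.** The strongest argument for a change is that a review is not a recording rule. A site that learns at Visit 3 of a Day 35 vaccination would find that Section 8.1.5.2, read literally, asks for no eCRF entry. The deviation route works only if someone recognizes the event as a deviation. Recording through the later of Day 30 or the draw would take a sentence and add no visit.

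The textual point stands: Section 8.1.5.2 and the Schedule of Activities are not aligned. What does not stand is the step from there to a weakened PP population. The text limits what must be recorded; it does not bar a later entry, and data management procedures are provided separately (Section 10.1.8). The exposure is named outright in Section 6.5, so a site that asks about vaccination and hears of one has little room to miss it. Extending the recording of every medication in children on long-term treatment would add data entry to cover one rarely expected vaccine.

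Day 30 could also be read as the nominal label of Visit 3, where the eVRC is reviewed and the device collected. That reading is possible but not conclusive, and the conclusion does not depend on it.

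The review is also marked at Visits 4 and 5, with no statement of what it collects beyond the SAEs and safety updates in Section 8.1.9. Those contacts come after the draw and cannot affect H1 or H2.

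**Conclusion.** No change to the plan is needed. This is a minor misalignment of wording: up to 14 days (13 on the other reading) without a routine recording requirement, for children bled after Day 30, and clearly relevant to one prohibited vaccine. The required vaccination review at the draw visit, the written deviation record and the deviation review before unblinding let analysts apply the PP exclusion as stated.

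This rests on sites carrying out the Visit 3 review and reporting what they find, as the protocol requires. The documents do not allow the effect on the GMT ratios to be estimated. The one-sided 2% illustration moves a ratio by 2.8% and leaves both expected lower bounds above their margins, narrowly so for the unique serotypes under a pessimistic pairing. Nothing in the plan suggests exposure at that level, or exposure confined to one arm of a blinded trial. Longer recording would tidy the text without a demonstrated effect on PP composition or on either primary hypothesis.
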